Maximum power of radio waves (mW)	250
Screen	10.1"
Connection	Internal Modem - SIM
Maximum number of exams that can be stored	1000
Cable length (mm)	battery charger->console= 905 power supply->battery charger =1180
Power supply weight (kg)	0,35
Power supply (V)	220 A.C.-12 D.C.

The signaling of the presence of intra-cranial lesion or abnormality is of the 'on-off' type. In the case of positive detection, the LED light clusters will signal this event by emitting a flashing red light signal; on the other hand, in the case of no negative result, they will signal this event by emitting a flashing green light signal. The report produced in PDF format is stored in the instrument and can be sent via internet connection to the prepared center at the end of the examination.

In TES-HT 100 devices there are components such as electromagnetic transducers, the control module, the electronics for transducer management, the power button (amber in color), the examination start/stop button (blue in color), and two sets of optical indicators that signal the status of the system at each stage of operation.

In terms of user interaction, the TES-HT 100 offers full functionality through the integrated physical buttons and also features a graphical touchscreen display, which allows for a graphical visualization of all phases of device operation

Figure 2- TES-HT 100 device

Table 3 shows the materials used in the manufacture of the TES-HT 100 device

Table 3 - Materials of the device

Materials Bulletin Device	
●	Mechanical structure
●	2 electromagnetic transducers
●	Electronic control board
●	Cables
●	Button with integrated amber-colored LED
●	Button with integrated blue color led
●	Management electronic board
●	Processing unit
●	RF signal generation system

● Display module, Human Interface Device (HID)
● Mechanical structure for containing the console
● Lithium-ion battery 12V, 10 A/h

Mechanism of action

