- 2) **Data processing and comparison** - At this stage, data are processed for each patient using appropriate ID and the result is linked to the respective diagnosis by the

relevant personnel at the institution hosting the survey.

The purpose of the clinical investigation is to commercialize the device on a national/international scale.

Description of the study

The single-center, open-label study that aims to clinically validate the TES HT100 as a screening tool for noncritical care patients attending the emergency department either for mild head injury or with neurological symptoms. The study involves the enrollment of two separate cohorts of patients:

- 1) 425 Patients with mild head trauma
- 2) 425 Patients with neurological symptoms not related to head trauma and not in a critical or life-threatening condition such as:
 - Syncope
 - Spatial disorientation and loss of balance
 - Speech disturbance and facial hemi-paresis
 - Visual impairment
 - Lack of memory and confusional state

All patients will follow the normal diagnostic-therapeutic procedure with priority access to CT examination according to severity and to which, as described below, only the examination with TES HT100 will be added, which has a maximum duration of 5 min (examination duration 4 min for acquisition and 1 min for data processing):

Patients with mild head trauma:

* the patient with mild head trauma following Acceptance Acceptance will be assisted and evaluated at Triage and will have a CT scan within 1 hr or more, followed by performing the temnographic examination with TES HT100, after signing the informed consent for participation in the study;

Patients with neurological symptoms:

* the patient following Acceptance Acceptance will be assisted and evaluated at Triage and a CT scan will be performed in order to exclude the possible presence of stroke and possible transfer via 118 to the Stroke Unit U.O.S.D. | A.O.S.G. Moscati. Temnographic examination with TES HT100 will be performed after the CT scan during the CT reporting phase, after signing the informed consent for participation in the study.

Information on the data collection form (Appendix A) will be collected for each patient.

Primary and secondary objectives

Primary objectives

- **Assess the diagnostic accuracy of the TES HT100:** Measure the sensitivity and specificity of the device in identifying brain lesions and structural brain changes in the cohorts of patients included in the study.

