Variables to be measured

TES HT examinations should be performed within 24 hours before or after the CT examination.

Systematic errors - bias

Systematic errors that may occur during the study are mainly related to the marked movement of the patient, who should avoid abrupt movements throughout the scan in order to reduce motion artifacts.

Patient selection

Patient inclusion criteria:

Group 1:

- age over 18 years
- acquisition of informed consent
- Patients referred to the emergency department for mild head injury

Group 2:

- age greater than 18 years
- acquisition of informed consent
- Patients afferent to the emergency department not for head trauma and not in a critical condition, with one of the following neurological symptoms:

- Syncope
- Spatial disorientation and/or loss of balance
- Speech disturbance and/or facial hemi-paresis
- Visual alterations
- Lack of memory and/or confusional state

Exclusion criteria for both cohorts:

- age less than 18 years
- pregnant women
- Metal plates or metal prostheses installed in the skull cap
- severe head trauma and/or with extensive lacerated contused areas
- patient in critical condition
- skull theca fracture
- failure to sign informed consent

The TES-HT device cannot be used in cases of metal plates or metal prostheses installed in the skullcap because their presence alters the outcome of the TES HT100 examination.

Number of patients expected to enroll

Considering that it is intended to prove the primary hypothesis that TES HT 100 succeeds in achieving a sensitivity and specificity of 90% when comparing to the outcome of the CT scan report, an AUC of 0.90 is obtained, a value indicative of its excellent reliability. Assuming that TES HT100 meets this performance, a sample size of about 384 subjects is needed to obtain a maximum error of 3% on the confidence interval in the 95% two-tailed test on AUC. In other words, the target AUC and sample size should allow 95% confidence that the AUC is within the range [0.87;0.93]. Given a 10% drop-out rate, a sample size of 425 subjects for each patient cohort is considered necessary. Although the sample size calculation was performed as was previously explained, we believe it is fair to consider, in the case where there is a large imbalance between positive and negative outcomes, a small adjustment on the precision of the AUC estimate. Specifically, we will consider a precision of 0.02 instead of 0.03.

Point of enrollment

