- 2) **Low risk to the patient** - The device does not emit ionizing radiation (as with CT scanning) and emission levels are well below reference limits.
- 3) **Short scan duration** - The duration of one measurement is 4 minutes.
- 4) **Small size and easily transportable** - The small size makes TES HT a device that can be used in all emergency situations and in places where rapid transport to a First Aid Center is difficult.

Thus, the device demonstrates positive cost-benefit and timely and beneficial results.

Statistics

To evaluate the performance of the device, statistical sensitivity and statistical specificity will be calculated. Statistical sensitivity indicates the device's ability to correctly identify positive cases, i.e., patients with brain injury (prior or post injury) and/or structural alteration of brain tissue. Statistical specificity indicates the ability of the device to correctly identify negative cases, i.e., patients with no brain injury (new or previous) and no structural alteration of brain tissue. All TES HT examinations will be compared with the CT scan report, which will sanction the actual presence or absence of structural alterations of brain tissue. Comparison criteria such as Receiver Operating Characteristic-Area under curve (ROC-AUC), sensitivity and specificity will be used as statistical validation tools. To this end, it is intended to demonstrate the primary hypothesis regarding a diagnostic performance of TES HT 100 not less than 90% ROC-AUC compared to the outcome of the CT report, while maintaining sensitivity and specificity of at least 80%. The minimum threshold of 90% is indicative of excellent instrument reliability.

To calculate the statistical sensitivity and specificity, the following data will be used:

	Brain injury present	Brain injury absent
Positive test	TP (True Positive)	FP (False Positive)
Negative Test	FN (False Negative)	TN (True Negative)
Total	TP+FN	FP+TN

- Number of true positive cases (TP): number of patients with brain injury (prior or posttrauma) and/or structural alteration of brain tissue identified

correctly by the device and confirmed by CT scan

- Number of false-negative (FN) cases: number of patients with brain injury (prior or posttrauma) and/or structural alteration of brain tissue not identified by the device but confirmed by CT scan

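### Neither the CT reader nor whoever codes the CT report is masked to the TES HT100 result, so the sole reference standard could drift towards the device and overstate accuracy

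*Protocol*

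**What the plan says.** **Design.** Description of the study begins: "The single-center, open-label study that aims to clinically validate the TES HT100". Masking of the CT reader is not mentioned there or elsewhere in the protocol.

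**Timing, neurological cohort.** The same section states: "Temnographic examination with TES HT100 will be performed after the CT scan during the CT reporting phase".

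**Timing, trauma cohort.** The patient "will have a CT scan within 1 hr or more, followed by performing the temnographic examination with TES HT100". This places the device exam after the scan but sets no order relative to the report.

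**Timing, general.** Variables to be measured states: "TES HT examinations should be performed within 24 hours before or after the CT examination".

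**Visibility of the device result.** Under Detailed description of the device, when the result is positive "the LED light clusters will signal this event by emitting a flashing red light signal"; a negative result gives a green light. A PDF report is stored in the instrument and can be sent over the internet when the exam ends. Description of the study puts the whole exam at 5 minutes at most.

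**Reference standard.** Primary end points and Statistics compare every device result with the CT report, "which will sanction the actual presence or absence of structural alterations of brain tissue". Under Statistics the target condition is broad: any brain injury, new or old, or any structural change in the brain.

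**Linkage.** Step 2 under Information regarding clinical investigation says that "data are processed for each patient using appropriate ID and the result is linked to the respective diagnosis by the" responsible staff of the host institution.

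**Recognised bias.** Systematic errors - bias names only patient movement.

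**The concern.** The device result is automatic, so knowledge of the CT can hardly change it. The exposed side is the reference. A CT report is a human reading, and turning a narrative report into present or absent under so broad a target condition takes judgement whenever the finding is slight or old. If the reader or the coder knows the device result, doubtful cases may be settled in its favour.

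This error does not average out. A false positive whose CT is called positive becomes a true positive; a false negative whose CT is called negative becomes a true negative. Both moves raise the primary accuracy estimates. Statistics sets the hurdle at an AUC of at least 0.90, with sensitivity and specificity of at least 0.80, and the study's stated purpose is to bring the device to market. Who knows what when the CT is read is a matter of study conduct, and no later analysis can recover an uninfluenced reading.

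**Working it through.** **1. The plan's own figure.** Number of patients expected to enroll gives about 384 evaluable subjects per cohort for an AUC of 0.90 with a 95% half-width of 0.03. Treating the AUC as a proportion, n = 1.96² × 0.90 × 0.10 / 0.03² = 384.1, which reproduces. With 10% drop-out, 384/0.90 gives 427 and 384 × 1.10 gives 423; the stated 425 lies between. These figures do not bear on masking, but the half-width of 0.03 is a useful yardstick for the bias.

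**2. The timing statements side by side.**
- Neurological cohort: the exam runs while the CT is being reported and lasts at most 5 minutes, so the result can exist before the report is signed.
- Trauma cohort: the exam follows the scan; before or after the report is left open.
- General window: up to 24 hours before or after CT. An exam before CT contradicts both cohort descriptions, which put the device after the scan. It would also make the device result available before any CT reading.

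In neither cohort does the schedule ensure that the CT report is complete before the device result is known.

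**3. Illustration of size.** Inputs:
- True sensitivity and specificity (Se = Sp) of 0.85: assumed, and below the 0.90 target.
- CT-positive share p of 5%, 10% and 30%. The values 5% and 30% are the protocol's literature figures for mild head trauma at GCS 15 and 13; 10% is an assumed value between them. For the neurological cohort the protocol gives no figure.
- Share f of discordant CT classifications moved to agree with the device: assumed, with no source in the documents.

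Formulas, in proportions of all patients:
- TP' = TP + f·FP and FP' = (1 − f)·FP
- TN' = TN + f·FN and FN' = (1 − f)·FN
- Se' = TP'/(TP' + FN') and Sp' = TN'/(TN' + FP')
- For an on/off test, AUC' = (Se' + Sp')/2

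Worked case, p = 0.30 and f = 0.10: TP = 0.255, FN = 0.045, FP = 0.105, TN = 0.595. Then Se' = 0.2655/0.306 = 0.868, Sp' = 0.5995/0.694 = 0.864 and AUC' = 0.866.

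Apparent AUC when the true AUC is 0.85:

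| Share moved (f) | p = 5% | p = 10% | p = 30% |
|---|---|---|---|
| 10% | 0.878 | 0.871 | 0.866 |
| 20% | 0.899 | 0.890 | 0.881 |
| 30% | 0.916 | 0.907 | 0.897 |

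For the 0.85 device to show 0.90, f must be about 20%, 26% and 32% respectively. Discordant patients number 0.15 × 384 = 57.6, so that is about 12, 15 and 19 patients per cohort.

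Against the planned half-width of 0.03, the upward shift is 0.016 to 0.028 at f = 10% and 0.031 to 0.049 at f = 20%.

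**4. Direction.** Moving only false positives at f = 20% gives 0.890 (p = 5%) and 0.868 (p = 30%); moving only false negatives gives 0.863 and 0.864. A device truly at 0.90 shows 0.916 to 0.910 at f = 10%. Every case is biased upwards.

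**The case against.** **Exposure is inferred.** Nothing in the protocol says that the radiologist sees the light, the screen or the PDF. The light is on the device beside the patient, radiology is not named as a recipient of the PDF, and CT follows the normal care pathway. A reader might infer that the CT report will be written with the device result in hand; the text gives timing, not communication. This stands, and it limits the point to a bias that the plan permits.

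**Linkage is not diagnosis.** A reader might also take step 2 to mean that hospital staff settle the diagnosis while looking at the device result. The text describes matching two records by ID, which alters neither. The risk lies in unmasked reading or coding of the CT. How a narrative report becomes positive or negative may be set in the data collection form (Appendix A), which is not in the text at hand.

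**One cohort only.** The reporting-phase timing is stated for the neurological cohort and should not be read across to the other. The trauma cohort is exposed for a different reason: no order is fixed, and the 24-hour window is open.

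**Size.** The shares needed to reach 0.90 are large. At 5% CT-positive and f = 20%, about 10.9 CT-negative patients would be called positive, out of about 29.6 apparent positives, or 37%. That is a demanding scenario, and at f = 10% the 0.85 device stays short of 0.90 throughout.

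**Traceability.** Quality assurance requires the time of each device exam and an audit trail of changes to clinical data, so later recoding would show. Influence on an unsigned report, or on the first coding, would not.

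What none of this answers is that the schedule lets the device result precede the CT report while the protocol keeps the two apart nowhere.

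**Conclusion.** The point holds as a gap in masking that should be fixed. In both cohorts the plan allows the device result to be known before the sole reference standard is read and coded. Any resulting error favours the device on sensitivity, specificity and AUC.

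The documents do not show that the bias will occur, and its size cannot be derived from them. The illustration rests on an assumed true Se = Sp of 0.85, an assumed share of discordant cases moved, and CT-positive shares that the protocol reports for mild head trauma only. On those terms the apparent AUC runs from 0.866 to 0.878 with 10% moved and from 0.897 to 0.916 with 30% moved. It would be wrong to conclude that a device below target would pass: that happens only when roughly 20% to 32% of discordant classifications move.

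**What to change.** In Description of the study, state for both cohorts that:

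1. The TES HT100 light, screen and PDF are not disclosed to the reporting radiologist until the CT report is signed.
2. Existing site staff unaware of the device result code each signed report as positive or negative against qualifying findings listed in advance.
3. That code is time-stamped and locked in the EDC before the device result is linked by ID.
4. Discordant cases are not re-read with the device result known.

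Reconcile the exam timing in Description of the study with the 24-hour window in Variables to be measured.

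The cost is protocol wording, an order of data entry, and some control in the emergency department over who sees the device result, including a coder kept unaware of it. No extra scan or patient is needed. The protocol adds the device exam to the normal pathway and gives its result no role in care, so withholding it from the CT reader does not conflict with the plan.

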The diagnosis of mild head trauma is mainly based on clinical manifestations such as loss of consciousness, amnesia, confusion, and altered mental status. The most common symptoms include confusion, amnesia, headache, dizziness, nausea and vomiting (5,6,7). Computed tomography (CT) is considered the gold standard for the diagnosis of head trauma (8).

To improve diagnostic accuracy and reduce unnecessary radiation exposure, clinical scores such as the Canadian CT Head Rule (CCHR), the New Orleans Criteria (NOC), and the

National Emergency X-Radiography Utilization Study II (NEXUS II) criteria to identify patients in need of CT (9,10). However, a systematic review of the literature estimated a prevalence of CT abnormalities of 5% among patients with GCS = 15 and 30% for those with GCS = 13 (11).

Importantly, despite the classification of mild head injury, this condition may hide important short- and long-term risks for the patient, underscoring the importance of more thorough evaluation and management of patients with this condition(12).

Other neurological conditions that may manifest with symptoms similar to those of mild head injury are given by: Syncope, for example, represents a temporary loss of consciousness due to transient cerebral hypoperfusion, and its prevalence in the general population is estimated to be around 3 percent per year (13).

Spatial disorientation and loss of balance can result from various neurological conditions, including stroke, vestibular diseases, and neurodegenerative disorders. It is estimated that about 30 percent of elderly patients aged 65-74 years and up to 50 percent of those over 75 years have balance disorders (14). These symptoms, if neglected, can lead to serious complications, underscoring the importance of timely and accurate evaluation.

Speech disturbances, such as aphasia, and facial hemi-paresis are characteristic symptoms of stroke. Early intervention within 3-4.5 hours after symptom onset can significantly improve functional outcomes and reduce the risk of permanent disability (15). Stroke is a major cause of disability and mortality, with a huge impact on both individual health and overall health care expenditures (16).

Approximately 30% of stroke patients have visual disturbances (17). Detailed assessment of these symptoms

is essential to determine the underlying cause and plan appropriate treatment in order to preserve visual function and prevent further neurological damage.

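### The ±0.03 precision on the AUC assumes that half the patients are CT-positive; no CT-positive share is stated, ±0.03 is not met at the 5% to 30% cited for mild head trauma, and the 0.02 allowance does not repair it

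*Protocol*

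**What the plan says.** The calculation is in the protocol section on the number of patients expected to enroll. It supposes that "TES HT 100 succeeds in achieving a sensitivity and specificity of 90"%, so that "an AUC of 0.90 is obtained". It then says that "a sample size of about 384 subjects is needed to obtain a maximum error of 3% on the confidence interval", at the 95% two-sided level. It spells this out: "should allow 95% confidence that the AUC is within the range [0.87;0.93"]. The enrolled number follows: "Given a 10% drop-out rate, a sample size of 425 subjects for each patient cohort is considered necessary".

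The same paragraph goes on to foresee a marked imbalance between positive and negative outcomes. For that case it names a precision of 0.02 in place of 0.03. No new sample size is given.

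Three other places bear on the point:

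- The device description and the description of the investigation say that the result is binary (on/off, or yes/no).
- The background on mild head trauma cites "a prevalence of CT abnormalities of 5% among patients with GCS = 15 and 30% for those with GCS = 13".
- The Statistics section counts as positive any brain injury, old or new, and any structural alteration on CT. It sets out to show an AUC of at least 90% with sensitivity and specificity of at least 80%, and it plans interim looks at 150 and 300 patients per cohort.

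**The concern.** The precision of an AUC depends on how many patients have the condition and how many do not. The sample-size paragraph uses neither number. It gives one total and one precision, as if the split did not matter, although the protocol's own background suggests that CT-positive patients may be a small minority of the head-trauma cohort.

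A reader of the paragraph would expect an interval of 0.87 to 0.93 in each cohort if the device performs as assumed. If positives are few, the interval is wider, and the loss falls almost entirely on sensitivity. For a screening device that is the measure that matters most, because it reflects missed lesions. The protocol also sets a floor of 80% for it.

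**Working it through.** **Inputs.** Sensitivity (Se) 0.90, specificity (Sp) 0.90, AUC 0.90, half-width 0.03, 95% two-sided (z = 1.96), 10% drop-out and 425 enrolled per cohort, all from the sample-size section. CT-positive share p of 5% and 30%, from the mild head trauma background. The values 10%, 20% and 50% are added to show the range.

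**Step 1: the plan's figure.** The single-proportion formula gives n = z² × 0.90 × 0.10 / 0.03² = 3.8416 × 0.09 / 0.0009 ≈ 384. The stated number reproduces. Drop-out: 384 / 0.9 ≈ 427, against 425 stated, a trivial difference.

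**Step 2: the formula for an on/off test.** Here AUC = (Se + Sp)/2. Se is estimated from the CT-positive patients and Sp from the CT-negative ones, so with N evaluable patients

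half-width = z × ½ × √[Se(1−Se)/(Np) + Sp(1−Sp)/(N(1−p))].

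With Se = Sp = 0.90, solving for ±0.03 gives N ≈ 384 / [4p(1−p)]. The denominator equals 1 only at p = 0.5, where the two formulas coincide. At any other share more than 384 patients are needed.

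**Step 3: what 384 evaluable patients give.** The half-widths for Se and Sp alone are z × √(0.09/number of patients in that group). The last column is the simulated chance that the estimated AUC falls between 0.87 and 0.93 when Se and Sp are truly 0.90.

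| CT-positive share | CT-positive patients | AUC | Se | Sp | Chance in 0.87–0.93 |
|---|---|---|---|---|---|
| 5% | 19 | ±0.069 | ±0.134 | ±0.031 | 62% |
| 10% | 38 | ±0.050 | ±0.095 | ±0.032 | 76% |
| 20% | 77 | ±0.038 | ±0.067 | ±0.034 | not run |
| 30% | 115 | ±0.033 | ±0.055 | ±0.036 | 93% |
| 50% | 192 | ±0.030 | ±0.042 | ±0.042 | 95% |

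Evaluable patients needed for ±0.03: 458 at 30%, 601 at 20%, 1068 at 10% and 2022 at 5%.

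**Step 4: if nobody drops out.** With all 425 evaluable, ±0.03 requires 4p(1−p) ≥ 384/425 = 0.904. That holds for p from about 34.5% to 65.5%, which lies above the whole cited range.

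**Step 5: the 0.02 allowance.** Even at p = 0.5, n = 3.8416 × 0.09 / 0.02² = 864.4, so 865 evaluable patients per cohort. At 30% the number is about 1029, and at 5% about 4550. Enrolment stays at 425.

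**Step 6: does the variance formula matter?** The Hanley–McNeil variance, meant for a continuous score, gives wider intervals with 384 patients: ±0.032 at 50%, ±0.039 at 30% and ±0.093 at 5%. The direction of the result does not depend on the formula chosen.

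**The case against.** The arithmetic is not in dispute. The case on the other side concerns how far it reaches.

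- **The protocol does not ignore imbalance.** A reader might infer that it does. It foresees imbalance and names a second precision, so the interval of 0.87 to 0.93 is not its only planning statement. This stands. But imbalance at a fixed size makes precision worse, and the text answers it with a tighter target and no added patients. Pooling the cohorts would come close to 0.02 (850 patients give ±0.020 at 50%), but the text sizes each cohort separately, and pooling would still give ±0.022 at 30% and ±0.046 at 5%.
- **The cited shares may not be those of this trial's positives.** They refer to CT abnormalities in mild head trauma. The Statistics section also counts prior lesions and any structural alteration, so the share could exceed 30%. For the cohort with neurological symptoms no share is given at all. This stands, and it limits the conclusion.
- **The worst case should not carry the argument.** The 5% figure is for GCS 15, and the mix of GCS scores is not stated. At 30% the gap is 0.033 against 0.030, with 115 positives. A reader might infer that sensitivity must rest on a few dozen patients or fewer; that is so only towards the lower end of the range.
- **Near balance the claim is nearly right.** At 40% the half-width is 0.0306. This also stands.

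**Conclusion.** The stated precision holds only under an unstated assumption: an even split for 384 evaluable patients, or a CT-positive share of about 35% to 65% if all 425 are evaluable. It is therefore not assured. At the only shares the protocol cites it is not met for the head-trauma cohort: the half-width is ±0.033 at 30%, a small shortfall, and ±0.069 at 5%, about 2.3 times the stated figure (0.069/0.03). The 0.02 allowance is not a remedy, because 425 patients do not reach ±0.02 at any share.

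A reader might go further and conclude that the trial will certainly miss ±0.03 in both cohorts, or that 425 is the wrong number of patients. The documents do not support either step. The share under the broad definition of a positive is not given and could be higher, and nothing is stated for the neurological cohort. What is wrong is the unconditional precision attached to the size.

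The result rests on Se = Sp = 0.90, a binary device result, and large-sample intervals, which are only approximate with about 19 positives.

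**What to change.** Keep 425 per cohort and rewrite the precision statement.

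1. Replace the single ±0.03 and the interval 0.87 to 0.93 with half-widths for AUC, sensitivity and specificity from the formula in step 2. Show them for each cohort over a range of CT-positive shares, for example 5%, 10%, 30% and 50%.
2. Beside each figure, give the number of CT-positive patients it rests on.
3. Delete the 0.02 sentence, since no size is provided for it.
4. Say that the stated precision will be updated from the CT-positive share observed at the planned 150-patient look in each cohort.

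The cost is a rewording of one section, with no extra patients. The downside is that the stated precision becomes less favourable.

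### Under imbalance the protocol changes the AUC precision from 0.03 to 0.02 but states no larger sample size; at the planned performance, 425 per cohort does not give 0.02 even at 50:50

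*Protocol*

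**What the plan says.** The Protocol section *Number of patients expected to enroll* plans on the device matching CT such that it "succeeds in achieving a sensitivity and specificity of 90% when comparing to the outcome of the CT scan report, an AUC of 0.90 is obtained". On that basis "a sample size of about 384 subjects is needed". The stated aim is "to obtain a maximum error of 3% on the confidence interval in the 95% two-tailed test on AUC", which the section restates as an interval from 0.87 to 0.93. It then allows for losses: "Given a 10% drop-out rate, a sample size of 425 subjects for each patient cohort is considered necessary". The section *Description of the study* gives the same 425 for each of the two cohorts.

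The sizing section closes with a qualification. The authors propose, "in the case where there is a large imbalance between positive and negative outcomes, a small adjustment on the precision of the AUC estimate". The adjustment is: "Specifically, we will consider a precision of 0.02 instead of 0.03".

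The section gives no sample size for 0.02, no threshold for a large imbalance and no assumed share of CT-positive patients.

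**The concern.** Precision and sample size are tied together: once the AUC and the case mix are fixed, choosing one determines the other. The protocol changes the precision and leaves the only stated size as it was. It does so for the case in which, at the planned sensitivity and specificity, the interval is wider than at 50:50.

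The ROC-AUC is the primary effectiveness endpoint, so this sentence describes how well the main result will be estimated. A reader who takes it at face value expects ±0.02 from 425 patients per cohort. A reader who takes it as a sizing rule expects a larger trial than the one described. Imbalance is also foreseeable in the trauma cohort: the section *Mild head trauma* cites CT abnormality in 5% of patients with GCS 15 and 30% of those with GCS 13.

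**Working it through.** **Inputs.** From *Number of patients expected to enroll*: sensitivity = specificity = 0.90, AUC 0.90, 95% two-sided interval (z = 1.96), half-width 0.03 or 0.02, 384 evaluable and 425 enrolled per cohort, 10% drop-out. From *Detailed description of the device*: an on/off result. Shares of CT-positive patients are assumptions that span the protocol's 5% to 30%, with 50:50 as the balanced case.

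**1. Reproduce the plan's figure.** The protocol prints no formula. The single-proportion formula returns its number:

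n = z² × A(1 − A) / d² = 1.96² × 0.9 × 0.1 / 0.03² = 384.2

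With 10% drop-out, 384 / 0.9 = 426.7, close to the stated 425.

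**2. Same formula at 0.02.**

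n = 1.96² × 0.9 × 0.1 / 0.02² = 864.4, so 865 evaluable; 865 / 0.9 = about 961 enrolled per cohort.

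The ratio is (0.03 / 0.02)² = 2.25.

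**3. Let the case mix vary.** For an on/off test, AUC = (sensitivity + specificity) / 2. With n evaluable patients and a share p CT-positive,

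half-width = 1.96 × 0.5 × √[0.09 / (np) + 0.09 / (n(1 − p))]

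At p = 0.5 this equals the formula in step 1. Example for n = 384, p = 0.10: 0.98 × √(0.09/38.4 + 0.09/345.6) = 0.98 × 0.0510 = 0.050.

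| CT-positive share (assumed) | Half-width, 384 evaluable | Ratio to 0.02 | Evaluable needed for 0.02 | Evaluable needed for 0.03 |
|---|---|---|---|---|
| 50% | 0.030 | 1.5 | 865 | 385 |
| 30% | 0.033 | 1.6 | 1,029 | 458 |
| 20% | 0.0375 | 1.9 | 1,351 | 601 |
| 10% | 0.050 | 2.5 | 2,401 | 1,068 |
| 5% | 0.069 | 3.4 | 4,550 | 2,022 |

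**4. Best case with no losses.** With all 425 evaluable and a 50:50 split, 1.96 × √(0.09 / 425) = 0.0285. The Hanley-McNeil variance, used as a check, gives a minimum of 0.0283 over all case mixes at 425. Neither reaches 0.02.

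**5. Read 0.02 as a planning input.** Suppose the cohort were enlarged to 865 evaluable so that imbalance would still leave 0.03. That requires

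p(1 − p) ≥ 1.96² × 0.25 × 0.09 / (865 × 0.03²) = 0.111, so p ≥ 0.127.

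Below about 13% positive even 865 is not enough; at 5% it gives about 0.046.

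**The case against.** The strongest reply is that the sentence stands in a section about numbers, straight after a calculation in which precision is an input. It may therefore mean that under imbalance the stricter 0.02 is entered and the size rises. On that reading the direction is sensible: 865 evaluable give 0.025 at 20% positive. A reader might infer that the adjustment plainly goes the wrong way, but that follows only if 0.02 is the precision to be achieved, and the text does not settle this. What does not survive is the consequence: no larger size is stated, and a factor of 2.25 is not a small adjustment.

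Other parts of the reply also stand:

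- The prevalences are not established for this study. The 5% and 30% concern CT abnormality in mild head trauma. The *Statistics* section also counts prior lesions and structural alterations as positive, which may be commoner, and no figure is given for the second cohort.
- It is tempting to say that any inequality pushes the interval beyond ±0.03. That is false. With 425 evaluable at 40:60 the half-width is 0.98 × √(0.09/170 + 0.09/255) = 0.0291. With sensitivity 0.95, specificity 0.85, 30% positive and 384 evaluable it is 0.98 × √(0.0475/115.2 + 0.1275/268.8) = 0.0292.
- The success criterion in *Statistics* is an AUC of at least 90% with sensitivity and specificity of at least 80%. It does not use the 0.02.

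Two further defences fail. Pooling both cohorts gives 2 × 384 = 768 evaluable and a half-width of 0.021 at 50:50 but 0.035 at 10% positive, and the protocol sizes the cohorts separately. The interim looks at 150 and 300 patients per cohort come with no rule in the protocol for changing the size.

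**Conclusion.** The point holds on either reading. As a precision to be achieved, 0.02 is not delivered: at the planned sensitivity and specificity of 0.90, 384 evaluable give 0.030 at best and 0.033 to 0.069 at 30% down to 5% positive, about 1.5 to 3.4 times the stated figure. As a planning input, 0.02 calls for about 865 evaluable (about 961 enrolled) per cohort, which the protocol does not provide and which would hold 0.03 only at a prevalence of about 13% or more.

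This rests on the inferred formula, which reproduces 384, on the planned performance and on assumed prevalences. The failure at 0.02 does not depend on the prevalence, because even 50:50 misses it. It does depend on the AUC: 425 balanced patients would reach 0.02 at an AUC of about 0.954 or more. A reader might infer that 0.02 is unattainable in any circumstances or that the success criterion is invalid; the documents support neither.

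**What to change.** Delete the last two sentences of *Number of patients expected to enroll* and put in their place:

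> The ±0.03 half-width assumes AUC 0.90 and about equal numbers of CT-positive and CT-negative patients. With 384 evaluable per cohort and sensitivity = specificity = 0.90, the expected half-width is about 0.033 at 30% CT-positive, 0.0375 at 20%, 0.050 at 10% and 0.069 at 5%.

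Do not state ±0.02 for 425 per cohort. The new wording keeps the acknowledgement of imbalance and attaches figures to it.

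The cost is two sentences and no extra patients; the stated precision becomes less favourable. If the sponsor did intend a larger trial under imbalance, the text must instead give the assumed prevalence and the resulting size, and the cost is then the additional patients in the last two columns of the table above.
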